HYPOTHESIS 1: BDD subjects will be differentiated from UD and HC subjects on measures of resting state corticoamygdalar connectivity and task-induced activation: BDD subjects will have lower lateral orbitofrontal (LOFC)-amygdalar connectivity but higher ventral anterior cingulate cortex (vACC)-amygdalar connectivity compared to UD and HC subjects. On measures of activation, while performing a happy emotion NoGo-Go task, UD subjects will have less dorsal ACC (dACC) activation compared to BDD and HC subjects.

SPECIFIC AIM 2: To investigate similarities and differences between BDD, HRUD and LRUD on measures of corticoamygdalar connectivity and activation.

HYPOTHESIS 2: HRUD subjects will display a pattern of corticoamygdalar connectivity and task-induced activation which will have similarities and differences with both BDD and LRUD subjects: HRUD subjects will have lower LOFC-amygdalar connectivity similar to BDD subjects but also lower vACC-amygdalar connectivity similar to LRUD subjects. On measures of activation, on the happy emotion NoGo-Go task, HRUD and LRUD subjects would have a similarly decreased dACC activation but on a negative facial emotion recognition task both HRUD and BDD will have lower insula activation compared to LRUD subjects.

EXPLORATORY AIM 3: Ultimately, only prospective data regarding which patients actually develop BD can validate the ability of the baseline imaging measures to predict a BDD or UD diagnosis. The main indicator of bipolarity is the presence of hypo(manic) symptoms. Beside conversion to (hypo)mania we will also measure occurrence of episodes of sub-threshold hypomania symptoms using the Young Mania rating Scale (YMRS) and the mania syndrome checklist of the Schedule for Depression and Schizophrenia (MSC-SADS) which has been recently used to study hypomania development in depressed patients. Besides looking at differences between converters and non-converters, an analysis will also be conducted of the correlation between peak change of YMRS and MSC-SADS scores as well as the slope of the change for mania symptoms ratings obtained over the course of the two years of follow-up. The data could be used to plan future large scale definitive studies.

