EXPLORATORY HYPOTHESIS 3: Baseline imaging measures will differ in converters to BD diagnosis vs. non-converters as between BDD and UD in Hypothesis 1. Peak change and slope of change in scores for YMRS and, MSC-SADS will correlate negatively with baseline LOFC-amygdala resting state connectivity and posterior insula activation on the face emotion recognition task and positively with vACC-amygdala connectivity and dACC activation on the happy emotion NoGo-Go task.

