connectivity besides the use of conventional fMRI regional activation paradigms of response to emotional stimuli. Preliminary findings (described below) from our studies support this hypothesis and provide rationale to conduct a definitive clinically relevant study.

2cii. Methods and Design:

We plan to recruit unmedicated 40 BDD, 60 HRUD, 60 LRUD as well as 40 HC subjects closely matched for age, gender and ethnicity for the study. We expect that at baseline 10% of subjects could be lost. During follow-up 15 - 20 % of HRUD and LRUD of patients may be lost before adequate data for development of (hypo)mania is collected. The number of subjects remaining will be adequate for statistical analysis proposed. For the exploratory aim, both the UD groups will be offered 24 months of antidepressant treatment with frequent mood assessments in the study. The other BDD and HC subjects will be followed up by phone for 24 months. During the 24 months all subjects will be rated on YMRS and the MSC-SADS for any periods suggestive of occurrence of hypomanic symptoms.

2c(ii)A. Human Subjects: The detailed inclusion and exclusion criteria and protection procedures are described in Human Subjects section E1a.

2c(ii)B. Recruitment and Timeline:

1. **Year 1:** Week 1 – 12: Training of study personnel and organization for initiation of study.
2. **Year 1 – Year 5:** Week 12 – Week 234: Recruitment of subjects and conduct of the study.
3. **Year 5:** Week 234 – Week 260: Continued follow-up of subjects and final data analysis and publication.

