where $h(t)$ is the hazard or rate of conversion at time (t), $h_0(t)$ is the baseline conversion rate and X_i for $i = 1, 2, \dots, p$ are covariates. The subjects will be followed in the fashion described in Table 3 with periodic assessments. The assumption of constant relative hazard rate over time will be tested and remedied if required following data transformation or by incorporating a piecewise constant hazard model. Based on this framework, we will test the significance of imaging and activation measures on the hazard rate. Our primary objective here is to identify those covariates that significantly affecting the hazard rate. The grouping of the UD (HRUD and LRUD) will be also treated as a separate covariate and put in the model as an indicator variable. To detect the progression of disease severity (episodes of (sub) threshold hypo(mania)) we will additionally use Young Mania Rating Scale (YMRS) and the mania syndrome checklist from the Schedule for Depression and Schizophrenia (MSC-SADS) between study visits over during follow-up. We will test the group difference between LRUD and HRUD using mixed-effects linear regression analyses⁹⁷ with repeated measurements taken over two years. Each model will include a random intercept and slope and fixed effects group, and time, as well as the stratification covariates. A likelihood ratio test will examine the incremental contribution of the group effect over time.

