Specific Aim 3: Using a conservative assessment of a 6% conversion rate for the LRUD group and 14% conversion rate for HRUD group, we calculate that with a sample size of 60 per group (HRUD and LRUD) we will have 80% power with type I error fixed at 0.05, under the assumption of 20% attrition rate in both groups, to detect statistically significant imaging measures as well as differential rate of conversion. We have used Bacsafra's⁹⁶ web based program to arrive at this power calculation. For sample size requirement to differentiate between HRUD and LRUD subjects via MSC-SAD and YMRS score peak-change and slope of change we will compare the mean baseline score and the mean peak scores using two sample t-test. Peak value for each group are extrapolated from usual values seen for YMRS iduring hypomania. Under the assumption of homogeneity among groups, for both the scales a sample of size 60 will be adequate even after adjusting for 20% attrition is adequate to ensure 90% power at alpha 0.05.

[figure not shown]

Fig. 8. Hypothetical YMRS peak score changes for HRUD and LRUD group over time

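### In exploratory Aim 3 the only planned HRUD–LRUD contrast in conversion sits in a Cox model that also tests imaging, so it does not estimate the crude 6% vs 14% difference used for power

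*Combined protocol and SAP*

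**What the plan says.** Section 2c(ii)la, Specific Aim 3, treats conversion from UD to BD as a time-to-event outcome and gives one Cox model with covariates X1 to Xp. Imaging and activation measures are tested for their effect on the hazard. On risk group it says: "The grouping of the UD (HRUD and LRUD) will be also treated as a separate covariate and put in the model", as an indicator variable. The only other HRUD–LRUD test in that section is a mixed-effects model, and its outcomes are the YMRS and MSC-SADS scores, not conversion. No log-rank test, group-only Cox model or comparison of proportions is given for conversion.

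Section 2c(ii)lb, Specific Aim 3, starts from two crude rates: "Using a conservative assessment of a 6% conversion rate for the LRUD group and 14% conversion rate for HRUD group". It then states "we will have 80% power with type I error fixed at 0.05, under the assumption of 20% attrition rate in both groups", and names two targets for that power: "to detect statistically significant imaging measures as well as differential rate of conversion".

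Section 1 links the same imaging measures to both group and outcome. Hypothesis 2 says "HRUD subjects will have lower LOFC-amygdalar connectivity similar to BDD subjects" and expects lower insula activation in HRUD than in LRUD. On vACC-amygdala connectivity and dACC activation it expects the two UD groups to be alike. Exploratory Hypothesis 3 says "Baseline imaging measures will differ in converters to BD diagnosis vs. non-converters as between BDD and UD in Hypothesis 1". It also expects LOFC-amygdala connectivity and posterior insula activation to correlate negatively with the change in mania scores.

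**The concern.** The power text refers to a marginal contrast: how often HRUD subjects convert compared with LRUD subjects. The only planned quantity that could serve as an answer is the coefficient of the group indicator in a model that also holds imaging. That coefficient describes the difference in hazard between an HRUD and an LRUD subject with the same imaging values. The two coincide only if imaging is unrelated to group or unrelated to conversion given group. The plan's own hypotheses make some overlap plausible for LOFC-amygdala connectivity and insula activation.

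The same applies in the other direction. With the group indicator in the model, an imaging coefficient is a within-risk-group effect, whereas Exploratory Hypothesis 3 compares converters with non-converters regardless of risk group.

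At stake is how the results are read. A null group term could be reported as no excess conversion in HRUD, and a null imaging term as no predictive value, when each had only been adjusted for the other.

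**Working it through.** **Inputs from the documents**
- Conversion 6% (LRUD) and 14% (HRUD); 60 per group; 20% attrition, so 60 × 0.8 = 48 per group; alpha 0.05; stated power 80% (section 2c(ii)lb, Aim 3).
- Follow-up of 24 months: "both the UD groups will be offered 24 months of antidepressant treatment with frequent mood assessments".
- HRUD–LRUD effect size for left LOFC-amygdala connectivity of −0.254, with 88% power at 60 per group (section 2c(ii)lb, Aim 2).

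**Assumptions, not in the documents**
- 6% and 14% are cumulative over 24 months, and tests are two-sided.
- The imaging HR per SD within risk group is 1.5, 2 or 3.

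**1. The plan's figure for the crude contrast.** HR = ln(0.86)/ln(0.94) = 2.44; log HR = 0.891. Expected events at 48 per group: 48 × (0.06 + 0.14) = 9.6. Schoenfeld: √(9.6/4) × 0.891 − 1.96 = −0.58, so power is 28%. The Freedman form gives 25.3% and a two-proportion test 25.5%. At 60 per group (12 events) these three methods give 31–34%. Reading the rates as annual makes the two-year risks 11.6% and 26.0%. Power is then 44–47% at 48 per group, and 65–68% in the most favourable case (60 per group, one-sided, no attrition). The stated 80% was not reproduced under any reading tried.

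**2. Size of the HRUD–LRUD imaging difference.** Read as SD units, 0.254 gives 28% power at 60 per group, not 88%. The difference that does give 88% is (1.960 + 1.175) × √(2/60) = 0.57 SD. The scale of the stated effect is therefore unclear, and both values are carried forward.

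**3. Group HR after adjusting for one imaging measure.** With d the HRUD–LRUD difference in SD and b the within-group log HR per SD, the approximation is: adjusted log HR = 0.891 − d × b. For example, d = 0.254 and HR 2 per SD give 0.891 − 0.254 × 0.693 = 0.715, or HR 2.04. This ignores the non-collapsibility of the HR, so the conditional HR was also found by calibrating each scenario to yield exactly 6% and 14%:

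| d (SD) | Imaging HR per SD | Approximate group HR | Log HR lost (approx.) | Calibrated group HR |
|---|---|---|---|---|
| 0.254 | 1.5 | 2.20 | 12% | 2.22 |
| 0.254 | 2 | 2.04 | 20% | 2.10 |
| 0.254 | 3 | 1.84 | 31% | 2.00 |
| 0.57 | 1.5 | 1.93 | 26% | 1.95 |
| 0.57 | 2 | 1.64 | 44% | 1.69 |
| 0.57 | 3 | 1.30 | 70% | 1.41 |

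Group-only Cox fits to large simulated data sets (20,000 per group) stayed at 2.36–2.61 across the scenarios run, so the group-only model does recover the crude contrast.

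**4. Power of the adjusted group term.** Schoenfeld with 9.6 events and the calibrated HRs gives 19–23% at d = 0.254 and 8–18% at d = 0.57.

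**The case against.** The strongest reply is that the plan never says the conversion difference will be taken from this coefficient. Aim 3 is titled as a search for imaging measures, its stated objective is to find covariates that affect the hazard, and section 1 contains no hypothesis about HRUD–LRUD conversion. The phrase on differential conversion occurs only in the power text. That is correct, and it narrows the point: the fault is a powered target with no matching analysis.

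The contents of the model are also not fixed. The plan does not say whether imaging measures enter together or singly. The paragraph on covariate adjustment uses forward stepwise entry, but its list names neither imaging nor risk group, so its reach is unclear. The figures above therefore use one measure at a time.

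The imaging half is weaker. Section 1, Exploratory Aim 3, already plans an unconditional comparison of converters with non-converters, although the statistical section gives no method for it. Asking what imaging adds to clinical risk group is a legitimate question, and a joint model suits it.

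A reader might infer that the group effect is adjusted away if Hypotheses 2 and 3 are true. The documents do not support that. Hypothesis 2 expects only two of the four measures to differ between HRUD and LRUD. Exploratory Hypothesis 3 is not stated within risk group, which is what attenuation requires. At 0.254 SD the loss is partial; near-total loss needs something like 0.8 SD with an HR of 3 per SD (calibrated group HR 1.10), for which the documents give no basis.

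**Conclusion.** The point holds as a mismatch of estimands in an exploratory aim. As written, the only planned HRUD–LRUD contrast in conversion is conditional on imaging, while the power statement concerns the crude 6% vs 14% contrast (HR 2.44).

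Attenuation is conditional, not certain. It arises if LOFC-amygdala connectivity or insula activation differs by risk group and also predicts conversion within risk group. The adjusted HR is then about 2.0–2.2 at 0.254 SD and about 1.4–1.95 at 0.57 SD. Both ranges rest on an assumed imaging HR of 1.5–3 per SD and on reading 6% and 14% as 24-month cumulative rates.

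A null group result should not be blamed mainly on the adjustment. With about 9.6 expected events the unadjusted comparison has only 25–28% power, so a null is the likely outcome with or without imaging terms. Nor should one infer that removing imaging restores the stated 80%.

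**What to change.** In section 2c(ii)la, Specific Aim 3, specify:

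1. HRUD vs LRUD conversion from a Cox model or log-rank test without imaging terms, reported as the differential conversion rate with its confidence interval.
2. Each imaging measure fitted first without the group indicator, as the unconditional contrast of Exploratory Hypothesis 3, and then with it, labelled as incremental value over clinical risk group. State whether imaging measures enter singly or together.
3. That the group coefficient of the joint model is conditional on imaging and is not read as the differential conversion rate.

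In section 2c(ii)lb, do not tie the group-only comparison to 80% power. Give its actual power, or present it as estimation only. For scale, 80% power for 6% vs 14% needs about 220 per group, or 220/0.8 = 275 with 20% attrition.

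The cost is a change of wording and one or two extra exploratory fits. No new data or subjects are needed for the change of analysis.

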Specific Aim 1: Differentiation between BDD and UD: We will conduct a one way ANOVA with the connectivity and activation measures as dependent variables to look at differences between groups (BDD and UD). The analyses will be similar to those in our previous studies^{41, 42}. The normality assumptions will be examined using the Kolmogorov-Smirnov test. Box-Cox type transformation methods will be employed if the normality assumption is violated for the outcome variable. To adjust for multiple comparisons accounting for multiple brain ROIs and ad-hoc comparisons conducted within an ANOVA model, Bonferroni adjustment will be used to control overall type I error rates (over-all significance level will be set to 0.05). A post ANOVA logistic regression based classification model will be constructed to build a classifier between BDD and UD. Specificity and sensitivity will be examined using receiver operating characteristics (ROC) curves. We will use leave-one out cross validation method to assess predictive performance of our classification model⁹⁶.

Specific Aim 2: Differentiation between BDD, HRUD, LRUD and healthy control: We will use corticoamygdalar connectivity, amygdalar-LOFC connectivity and ACC Activation in Emotion to perform one-way ANOVA among all four groups. Prior to the analysis, each of these variables will be transformed (using the Box-Cox transformation) so that they will made as close to Gaussian as possible. The normality assumptions will be examined using the Kolmogorov-Smirnov test. Specificity and sensitivity will be examined as in Aim 1.

Specific Aim 3: Identification of imaging measures significantly affecting the rate of conversion from UD to BD: The conversion of UD subjects into BDD is defined as the time to event phenomenon and will be modeled using Cox-proportional hazard model given by,

$$\log(h(t)) = h_0(t) + \beta_1 X_1 + \beta_2 X_2 + \dots + \beta_p X_p$$

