Adjusting for covariates: These include behavioral rating such as, attentional variables such as response time, and accuracy of response, and changes in physiological ratings; demographic variables such as age, gender, and ethnicity; scores on behavioral measures such as anxiety; treatment with concomitant medications such as atypical neuroleptics during the study; treatment history, substance abuse, and trauma history; and structural variables such as whole brain and ROI volumes. We will first identify the covariates with highly correlated with the outcome measures. Next, from this pool of highly correlated covariates to guard against multicollinearity and to conserve for degrees of freedom to ensure that we have sufficient power. To control for potential confounding effects from these covariates and not over-fit in any of our models, we will use the forward stepwise regression model building approach - so that only one covariate will be included at a time in the model - which allows us to screen out covariates that are not related to our outcome measures by using an elevated p-value ($p=0.1$) and reserve statistical power to a limited number of variables that are shown to be associated with outcome measures in our data⁹⁸.

2c(ii)lb. Sample size and power consideration: Preliminary data obtained from BDD and UD subjects were compared with healthy subjects to obtain estimates of sample size at significance level set at 0.05. Proc Power of SAS software is used to estimate the sample size.

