Specific Aim 1: We used our pilot data for Left LOFC-amygdala connectivity measure. This data yielded an effect size of 0.27 for difference between BDD and UD group. 40 samples in the BDD and 120 samples in UD group will give us more than 80% power to detect an effect size as low as 0.15 for the difference in Left LOFC-amygdala connectivity between two groups. Probability of type 1 error (alpha) was set always at 0.05. For ACC-left amygdalar connectivity measure, the effect size is 0.482. With previous mentioned sample size for each group we will have 90% power to detect an effect size as low as 0.3. Similar conclusion can be made for ACC activation in NoGo-Go task for which the data yielded an effect size of 0.726 for difference between BDD and UD group. Our proposed sample size is enough to detect the difference of effects with a power close to 90% at a significance level of 0.05. Even with 20% attrition rate (i.e. 32 BDD and 96 MDD) this sample size is large enough to ensure 80% power at alpha 0.05.

Specific Aim 2: For comparisons among BDD, HRUD, LRUD and healthy subjects all three connectivity and activation measures produce power more than 80% for 40 subject per group to detect a significant difference. In the present case with 40 BDD, 60HRUD and 60 LRUD samples the power calculation is little involved, nevertheless increased sample size ensures more than 80% power at alpha= 0.05. To compare HRUD vs. LRUD left LOFC-amygdala connectivity measure yields an effect size of -0.254. For 60 subjects/group this produces 88% power at alpha 0.05.

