3. HUMAN SUBJECTS

E1a. Human Subjects Characteristics:

The human subjects age range 16 - 30 yrs (inclusive) involved in this study will be - 40 BDD, 60 HRUD, 60 LRUD and 40 healthy control subjects matched as a group for age, gender and ethnicity who will be studied at baseline. BDD and UD subjects will be matched for depression severity at the time of the scan. However, it is likely that, by definition the BDD and UD subjects will be different in terms of other illness characteristics such as duration of illness, number of episodes, and history of alcohol and substance abuse. We will treat those illness variables as covariates in our statistical analysis (as described in section 2c(ii)1a above) to take into account the potential confounding effects of some of these variables.

Inclusion criteria for BDD patients:

1. Ages 15 - 30 years (inclusive) and able to give voluntary informed consent (consent will be taken from both parents and child for children under the age of 18)
2. Satisfy criteria for Diagnostic and Statistical Manual 4th edition (DSM-IV-TR) for Bipolar I or II disorder
3. Satisfy criteria for DSM-IV depressive episode-current
4. 17-item Hamilton Depression Rating Scale > 15 but < 25;
5. Young Mania Rating Scale score < 10
6. Satisfy criteria to undergo an MRI scan based on MRI screening questionnaire.
7. Able to be managed as outpatients during the study as ascertained by the following –
 - i. Clinical Global Severity Scale < 5 i.e. moderately ill;
 - ii. No significant suicidal or homicidal ideation or grossly disabled.

Inclusion criteria for All UD patients:

1. Ages 15 - 30 years and able to give voluntary informed consent (consent will be taken from both parents and child for children under the age of 18).
2. Satisfy criteria for DSM-IV-TR Major Depressive Episode using a Structured Interview
3. Never met criteria for mania or hypomania
4. 17-item Hamilton Depression Rating Scale score (HDRS) > 15 and < 25.
5. Young Mania Rating Scale (YMRS) score < 10
6. Satisfy safety criteria to undergo an MRI scan
7. Able to be managed as outpatients during the study as ascertained by the following –
 - i. Clinical Global Severity Scale < 5 i.e. moderately ill;
 - ii. No significant suicidal or homicidal ideation or grossly disabled

Additional Inclusion criteria for High Risk UD (HRUD) patients beside the inclusion criteria for UD:

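### Covariates for Aims 1–2 are chosen by their association with the outcome alone, so illness variables that the protocol says it will adjust for can drop out and the adjusted group tests may exceed 0.05

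*Combined protocol and SAP*

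**What the plan says.** The paragraph on adjusting for covariates in section 2c(ii)la (Statistical Analysis) lists many candidates: task performance, physiological ratings, demographics, anxiety, concomitant medication, treatment history, substance abuse, trauma and brain volumes. It then gives two steps.

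- Screen: "We will first identify the covariates with highly correlated with the outcome measures". No cut-off is given. The next sentence, on multicollinearity, has no main verb, so the handling of the resulting pool is not stated.
- Selection: "we will use the forward stepwise regression model building approach", in order to "screen out covariates that are not related to our outcome measures by using an elevated p-value" of 0.1. The stated aim is "To control for potential confounding effects from these covariates and not over-fit in any of our models".

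The paragraph names no covariate that is always kept. It does not say whether the group term is in the model during selection.

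Three other places promise adjustment:

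- E1a (Human Subjects Characteristics) expects BDD and UD to differ in illness duration, episode count and alcohol or substance history. It says "We will treat those illness variables as covariates in our statistical analysis", and points back to the statistical section.
- The DIGS entry in 2c(ii)G (Rating Scales) puts prior medication and the medication-free period into an analysis of covariance.
- The life and childhood events entry in 2c(ii)G says those scores serve as covariates.

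Neither 2c(ii)G entry mentions selection.

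Aims 1 and 2 are described as one-way ANOVAs. Under Aim 1 the "over-all significance level will be set to 0.05", with a Bonferroni adjustment for regions and post-hoc comparisons. The adjustment does not cover covariate selection.

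**The concern.** The groups are observational, so adjustment has to deal with variables that differ by group. A rule that looks only at the outcome association can miss a variable that differs strongly by group but is only weakly related to the imaging measure. Several such omissions add up to a spurious group difference. If group is already in the model, it takes up part of each confounder's effect, and the confounder is then more easily left out. Because selection is repeated for each measure, two connectivity measures may be adjusted for different things, and a contrast between them may reflect only that. At stake are the level of the adjusted tests in Aims 1–2 and the comparability of the imaging measures.

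**Working it through.** **Inputs from the documents.** Forward entry at p<0.1; overall alpha 0.05 (sidedness not stated, two-sided assumed); "40 samples in the BDD and 120 samples in UD group" for Aim 1; 60 vs 60 for HRUD vs LRUD.

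**Assumed, because the documents do not give them.** 15 candidates (13 items counted from the covariate paragraph, plus illness duration and episode count from E1a); 0, 1 or 3 true confounders; group imbalance δ of 0.5 or 0.8 SD; covariate–outcome correlation ρ of 0.10 to 0.30.

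**Model.** The outcome is y = b·ΣC_j + e over k confounders, with b = ρ/√(1−kρ²). Each confounder is shifted by δ in one group. There is no group effect once the confounders are held fixed. Each run selects covariates and then tests group by OLS at 0.05 (2,500–8,000 runs per setting; Monte Carlo standard error about 0.3–0.9 percentage points).

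**Nominal level.** With no confounding and no selection, the error is 5.2% (40 vs 120) and 4.8% (60 vs 60), consistent with the plan's 0.05.

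**Hand check of the confounding.** Take k=3, ρ=0.15, δ=0.5.

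- b = 0.15/√(1−0.0675) = 0.155.
- The unadjusted shift is 3×0.155×0.5 = 0.233.
- The SD of y within group is √(1+3×0.155²) = 1.036, so the standard error is 1.036×√(1/40+1/120) = 0.189.
- The shift is 0.233/0.189 = 1.23 standard errors, and the rejection probability is about 23%. Simulation gives 23–26%.

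**How often a confounder is missed** (40 vs 120, three confounders, group in the model, no first screen), as one minus the share kept:

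- ρ=0.10: 1−0.349 = 65%
- ρ=0.15: 1−0.604 = 40%
- ρ=0.20: 1−0.829 = 17%
- ρ=0.30: 1−0.994 = under 1%

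**Type I error (%), 40 vs 120, no first screen:**

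| Confounders, δ, ρ | No adjustment | Stepwise, group in | Stepwise, group last | Confounders fixed |
|---|---|---|---|---|
| none | 5.2 | 5.9 | 5.1 | 5.2 |
| 1, 0.5, 0.15 | 7.3 | 7.6 | 6.0 | 5.8 |
| 1, 0.8, 0.15 | 11.1 | 9.2 | 6.2 | 6.0 |
| 3, 0.5, 0.10 | 12.2 | 8.9 | 5.6 | 5.0 |
| 3, 0.5, 0.15 | 24.1 | 9.1 | 5.2 | 4.9 |
| 3, 0.8, 0.15 | 48.2 | 11.7 | 4.6 | 4.3 |
| 3, 0.8, 0.20 | 73.8 | 9.3 | 4.6 | 4.7 |
| 3, 0.8, 0.30 | 97.8 | 5.7 | 4.7 | 5.1 |

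A separate set of runs with three confounders at 0.8 SD and slopes of 0.10–0.15 gave 11.5–14.4% with group in the model, and 1.3–1.9 of the three confounders missed per run. At 60 vs 60 the confounded settings that were run gave 7.3–10.1% with group in and 4.9–6.0% with group last.

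**With the plan's first screen, 40 vs 120, δ=0.5 (%), group in / group last:**

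| Confounders, ρ | Cut-off at absolute r of 0.2 | Cut-off at absolute r of 0.3 |
|---|---|---|
| 1, 0.15 | 5.6 / 5.6 | 6.4 / 6.4 |
| 3, 0.15 | 10.3 / 10.1 | 20.5 / 20.5 |
| 3, 0.20 | 7.8 / 7.8 | 25.7 / 25.7 |

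Other runs at the 0.2 cut-off gave about 15%, whether or not group was in the model. Once a strict screen is applied, the timing of the group term hardly matters.

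**The case against.** Five points can be made for the plan.

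- **Near-nominal reading.** The text can be read as selecting covariates on the outcome before group enters. With no first screen, the error is then about 5–6%. This stands, and so a reader who infers that the Aim 1 and Aim 2 p-values simply lack their 0.05 level goes further than the documents allow. But the plan does state a first screen, and it leaves open both the cut-off and when group enters.
- **Stepwise is generally better than none.** This stands too. In the first table, no adjustment gives 12–98% with three confounders, against 6–12% for stepwise with group in the model. With no confounder or a single weak one, the two are about equal. The criticism is not a case for dropping adjustment.
- **The ANOVA may be the confirmatory test.** Aims 1 and 2 name a one-way ANOVA, and adjustment is described separately. If the unadjusted ANOVA is confirmatory, selection does not touch its p-value. The point therefore concerns the adjusted tests, and an unadjusted test leaves the expected imbalances uncorrected.
- **The promise may be weaker than it sounds.** E1a cites the statistical section, so its illness variables may be meant only as candidates. On that reading E1a does not contradict the rule, but adjustment for the expected imbalances is not assured. The two 2c(ii)G statements still sit badly with the rule.
- **Some protection exists.** The elevated entry level and the group matching on age, gender, ethnicity and, for BDD and UD, depression severity all help. They do not cover the illness history that E1a expects to differ.

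A reader might also infer that medication given during follow-up will enter the baseline imaging models. The covariate list is shared by all aims, including the follow-up aim, so the documents allow this but do not say it.

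**Conclusion.** The concern holds in a conditional form. The selection rule ignores association with group, can drop variables that E1a expects to be imbalanced, and is not reconciled with the adjustment promised in 2c(ii)G.

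The size depends on assumed confounding and on steps the plan leaves open. Under weak confounding, the error is about 7–14% with group in the model during selection. With the first screen it is about 5–15%, and above 20% in some settings at a cut-off of 0.3. It is near 5–6% if there is no screen and group enters last, if there is no confounding, or if confounders are strong enough to be selected almost always without a screen. With the confounders fixed in advance it is about 5–6%, within simulation error.

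No single figure should be quoted as this study's error rate, because the documents give neither the imbalances nor the slopes.

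**What to change.** For Aims 1–2, replace stepwise selection with one fixed covariate set per type of comparison, used for every imaging measure and written down before group-labelled data are analysed.

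- **Patient-only comparisons** (BDD vs UD; BDD, HRUD and LRUD): always include illness duration, episode count, alcohol or substance history, and the prior-medication and life-event covariates already promised, with age and gender.
- **Models with healthy controls**: use age, gender and ethnicity. Leave out HAM-D, which would nearly coincide with patient status, and illness history, which does not apply to controls.
- Keep medication given after the baseline scan out of the baseline imaging models.
- Label any stepwise model exploratory.
- State whether the adjusted model or the one-way ANOVA is the main test, and align E1a and the two 2c(ii)G statements with the new list.

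Fixing only age, gender and HAM-D would not do. These are already largely matched. Taken as balanced between groups, that set gave 35% against 36% unadjusted (three confounders, 0.8 SD) and 25% against 26% (four confounders, 0.5 SD), which is worse than the stepwise rule.

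The cost is SAP wording and a few degrees of freedom in models with 160 (40+60+60) to 200 (adding 40 controls) subjects. The downside is that the data can no longer suggest a covariate for the main model.
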